All MITU clinical research complies with NIH regulations, and with U.S. and Tanzanian laws. Tanzania has a National IRB, which has a US Federal Wide Assurance (FWA) and OHRP Registration FWA00002632. The Weill Cornell Medicine IRB FWA number is FWA0000093.

The Tanzanian National IRB has jurisdiction over all research conducted in Tanzania. All clinical trials conducted in Tanzania must be approved by the Tanzanian National IRB. The Tanzanian National IRB is recognized by and collaborates closely with Regional Medical Officers and hospital directors throughout Tanzania. The Tanzanian National IRB is chaired by [name]. The IRB has fifteen members who are all independent of MITU and include clinical scientists, biomedical scientists, social scientists, a lawyer, an unaffiliated community representatives and representatives of both Muslim and Christian faith-based organizations. The Tanzanian National IRB requires protocol documents to be submitted at least 10 days in advance of each meeting. Each package contains: 1) a cover letter with the PI's signature certifying that the study will comply with good clinical practices (GCP) requirements; 2) a study protocol; 3) all questionnaires, surveys, informed consents, and education material in both English and Tanzanian Kiswahili; the Tanzanian National IRB meets every third Saturday of the month. A written response is provided within one week. [name] (PI) has served on a local IRB in Mwanza, Tanzania since 2014 and has practical experience with the nature and application of IRB regulations in Tanzania.

The Weill Cornell Medicine IRB requires documents to be submitted at least 14 days prior to the meeting. Documents that are required for regular applications and expedited applications include: 1) protocol application; 2) informed consent/assent forms in English and Kiswahili; 3) subject recruitment materials and study advertisements, in English and Kiswahili; 4) study specific financial disclosure form for all personnel; 5) Human Research Billing Analysis Form (HRBAF); 6) all data collection sheets, surveys, questionnaires, psychological tests, and interview forms read to or completed by the research volunteer must also be submitted in Kiswahili and English; 7) FDA correspondence; 8) sponsor protocol; 9) investigator's brochure and package inserts; 10) associated grant application; and 11) local language verification statement for all translated documents. Responses to IRB questions or deferrals are reviewed at the following board meeting.

a. Recruitment and Informed Consent

Informed Consent: Eligible adults will provide written informed consent. **Those who do not participate will still be provided with free HIV care and counseling at the hospital and free HIV clinic care.** Research consent forms will be approved by the Tanzanian National IRB and the Weill Cornell IRB. Forms will be translated into Kiswahili and back translated.

The study investigators, particularly [name] (co-investigator), have published extensively on the optimal strategies to assure participants' comprehension of the informed consent form and their voluntary participation in research in resource-limited settings (1-4).

The consent form will include information on study purpose and study procedures, possible risk or discomforts, possible benefits, alternative procedures, confidentiality, right to refuse or withdraw and security of care if they withdrawal. The consent form will also contain information about what participants should do if they have questions about the study; if they wish to withdraw as a participant; if they have concerns about their rights as a study participant; or if they believe they have been harmed by the study including social harms of loss of confidentiality or stigma. The research assistant will emphasize that enrollment is voluntary and that the choice to participate will in no way influence the quality of services they may receive in the hospital or at the HIV clinic. Ample opportunity will be provided to potential participants to ask questions. Consent forms will include contact information for the local investigators.

Once the participant fully understands the study details and expresses a wish to participate, the research assistant will provide a consent form to sign and date in the space provided. The research assistant will also print and sign her name and date the form. The participant will be offered a copy of the consent form to take home. If the participant is illiterate, a thumb-print will be obtained.

Recruitment and informed consent: MITU is committed to the ethical conduct of research following the international standards of the Helsinki Declaration and US Federal Registry. MITU has established procedures to assure the **voluntary informed consent** of research participants. Prior to enrolling in a research trial, all potential volunteers are educated about the voluntary nature of participating in a trial; they are also educated regarding delivery of free HIV care in Tanzania, regardless of their participation in a study. Participants are informed of alternatives to enrolling in the study and are informed that declining participation will not impact on their access to care at the facility. Volunteers receive counseling concerning all study procedures, number of visits, risks and benefits of study participation, and alternatives to study participation. Ample time is given to each volunteer to discuss the study and to ask and receive answers to all of their questions and concerns. Each volunteer is given a copy of the signed consent for their records.

b. Protection Against Risks

The following measures will minimize study risks:

- A. **Loss of Confidentiality:** All samples and subject data will be coded at MITU. Each subject will be assigned a study identification number consisting of a unique code unrelated to any patient identifying information, as per Good Clinical Practice guidelines. Any identifiers linked to the participant will be secured and only available to staff at MITU, to ensure subject confidentiality. All source documents will be kept in locked file cabinet. MITU computers and servers are protected by firewall protection and are only accessible with a password. Study staff will be trained in Good Clinical Practice regarding maintaining confidentiality. We will provide intensive counseling and education to all participants on the importance of confidentiality. Participants will be asked to report any breeches in confidentiality and these will be reported to the IRBs and DSMB. During home visits, if asked by friends or neighbors about the purpose of their visits, the social workers will identify themselves as being part of a research study to improve post-hospital outcomes for patients who had been admitted to a study hospital. No mention of HIV will be made. In our formative research, HIV-infected patients informed us that friends, neighbors and relatives had all been aware of their hospital admission and the hospital admission itself was not associated with stigma.
- B. **Social Harms:** Study staff will be sensitized to the challenges experienced by HIV-infected adults as a vulnerable population. They will be trained on how to respond to any social harm reported by a participant. Staff performance will be monitored by the research and intervention coordinators, [name] and [name], during quality assurance assessments to ensure minimization

of social harms. Of note, [name] served as the social worker for the pilot intervention study and has 2 years of experience monitoring for social harm from this intervention. Doctors [name], [name], [name] will be available to assist the study staff in responding to any event that requires further management. Tanzanian HIV clinics routinely educate all HIV patients clinic on the importance of confidentiality and not sharing information with other patients. Participants will be encouraged to report any adverse event. Study staff will ask each participant about social harms including loss of confidentiality and stigma at each study visit. All adverse events will be detailed in source documents and reported on standardized adverse event forms.

C. Discomfort: As part of the informed consent process, all potential participants will be instructed that they do not have to disclose personal information that they are uncomfortable sharing and that they can withdraw from the study at any time.

3. Potential Benefits of the Proposed Research to Human Subjects and Others

The proposed study has the potential to improve survival of hospitalized HIV-infected patients in Tanzania. People from other African countries may benefit in the future from the knowledge gained in this study.

4. Importance of the Knowledge to be Gained

The results of this study may provide evidence for a new model of HIV care and treatment for HIV-infected adults. Outcomes will be used to better understand factors influencing linkage to primary HIV care and survival. [name], the Tanzania Site PI of this proposal, is a senior advisor to the Tanzanian Ministry of Health. He will work with the Ministry to create an implementation plan so that our social worker intervention can become a national model of care. An effective social worker intervention can be adapted to similar resource-limited settings. **Nurses or community health workers** could fill the role of the social worker in other settings depending upon availability of health care workers.

5. Data and Safety Monitoring Plan

The following monitoring steps will be taken to monitor and ensure the safety of research volunteers:

- A. The study and consent forms must be approved by Institutional Review Boards in Tanzania and Weill Cornell Medicine prior to the start of the trial.
- B. The Principle Investigator will receive a daily log of adverse events and will review this log each week with the local study team and collaborators.
- C. The study team is responsible for reporting all severe adverse events suffered by study participants to the IRBs and DSMB within 24 hours of knowing of the event.
- D. The Principle Investigator must renew IRB approval every year through submission of an annual update including a description of all adverse events.
- E. A Data Safety Monitoring Board (DSMB) will ensure the safety of trial participants through monitoring study procedures, implementation, study findings and review of all adverse events including social harms. The DSMB is described in full in the next section.

The successful completion of this study has the potential to dramatically improve survival for HIV-infected adults in Tanzania and other resource-poor countries.

References

1. Fitzgerald DW, Behets FM-T. Women's health and human rights in HIV prevention research. *Lancet*. 2003 Jan 4;361(9351):68–9.
4. Joseph P, Schackman BR, Horwitz R, Nerette S, Verdier RI, Dorsainvil D, et al. The use of an

educational video during informed consent in an HIV clinical trial in Haiti. *J Acquir Immune Defic Syndr.* 2006 Aug 15;42(5):588–91.

Data Safety and Monitoring Plan

The Data Safety and Monitoring Board will ensure the safety of trial participants through monitoring study procedures, implementation, study findings and review of all adverse events including social harms. It will be chaired by [name] (MD), Assistant Professor of Medicine at Harvard Medical School. [name] has conducted HIV research for over 10 years in resource-limited settings. She recently completed an NIH-funded clinical trial of same-day HIV testing and ART initiation in Haiti (1).

[name] (Chair of the Department of Internal Medicine at the Bugando Medical Centre) has 10 years of experience as an HIV clinician and researcher in Tanzania. Before become the Chair of Medicine he was employed as physician on the medical wards of Bugando and as a doctor in the Bugando HIV clinic. His research is particularly focused on improving survival for hospitalized HIV-infected adults.

[name] (Director General of the National Institute of Medical Research in Mwanza, Tanzania) is an internationally recognized public health expert with 30 years of experience conducting HIV research in Tanzania. He has served as site PI for numerous clinical trials performed in Mwanza. [name] is also a member of the Tanzanian National IRB.

The DSMB will meet before enrollment starts to review the study protocol for protection of human participants. The DSMB will then meet every six months via Skype. Prior to their meeting, they will receive summary reports of study progress, all adverse events including loss of confidentiality, stigma, and any other social harm reported by a study participant. Any severe adverse event will be reported to the DSMB Chair, [name], within 24 hours of documentation by study staff. After each meeting, the DSMB will provide a written report on the status of the study and their recommendations for any modifications of the study. This report will be provided to the PI and IRBs. Of note, we have not planned an interim analysis because by the time half the cohort has been enrolled and followed for one year to the primary study endpoint, the other half will have been enrolled, discharged from the hospital, and the 3-month intervention will be complete.

The DSMB has the right to halt the study for safety concerns at any time. The study team, the Weill Cornell and Tanzanian National IRBs, and the DSMB will work closely together to assure the conduct of this study according to NIH regulations for the protection of human subjects and to minimize risks to all study participants.

Reference

INCLUSION OF WOMEN AND MINORITIES:

Women will be included in all study activities. We will recruit Tanzanian adults ≥ 18 years living in Mwanza. Based upon the characteristics of our patient population in Tanzania, an estimated 50% will be women and greater than 99% of the participants will be black and of African descent.

INCLUSION OF CHILDREN:

No person < 18 years of age will be included in the study.

References:

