Linkage and other steps in the HIV care continuum: Linkage will be defined as having at least one visit to the outpatient HIV clinic. Twelve-month retention will be defined as being alive and having a clinic visit between 11 and 13 months. Twenty-four-month retention will be alive with a visit between 23 and 25 months. Adherence will be measured with a 3-day recall questionnaire and by reviewing pharmacy refill records and calculating the proportion of prescribed days of ART which are actually picked up over time. HIV RNA levels are measured routinely at the Mwanza HIV clinic at 6, 12 and 24 months, and we will retrieve results from the EMR. HIV viral suppression will be defined as a plasma HIV RNA level <1,000 copies/ μ l (15). Participants who have \geq 1,000 copies/ μ l or who do not have plasma HIV RNA level measured will be considered **virologic failures**.

TABLE 3.
RESEARCH SCHEDULE, MEASURES, AND OUTCOMES

		Month of Research Visits								
		0	3	6	9	12	15	18	21	24
RESEARCH ASSISTANT COMMUNICATIONS										
Face-to-face visits		X				X			X	
Phone call			X	X	X		X	X	X	
DEMOGRAPHICS										
Age, sex, education		*	X							
Economic status (weekly income)		*	X			X			X	
MEDICAL HISTORY										
Date of HIV diagnosis		+	X							
Prior ART use		+	X							
WHO stage		+	X	X	X	X	X	X	X	
Physical measures (height, weight, blood pressure)		+	X			X			X	
Alcohol use (AUDIT) (65,67,68)		*	X			X			X	
Depression (PHQ-9) (64)		*	X			X			X	
PSYCHOSOCIAL FACTORS										
Employment (ARTAS Baseline and Follow-up Tools) (69)		*	X			X			X	
Traditional health beliefs (HIV Knowledge Questionnaire) (70,62)		*	X			X			X	
Self-efficacy (HIV – Adherence Self-Efficacy Scale) (71)		*	X			X			X	
Transportation (ARTAS Baseline and Follow-up Tools) (69)		*	X			X			X	
Stigma (AIDS-Related Stigma Scale) (72,73)		*	X			X			X	
Social support (SPS-10) (63)		*	X			X			X	
Perceived need for HIV services (ARV Medications Attitude Scale – 15) (74)		*	X			X			X	
Physical Weakness (SF-12) (75,66)		*	X			X			X	
PRIMARY OUTCOME										
Death		¢		X	X	X	X	X	X	
STEPS IN HIV CARE CONTINUUM										
Linkage to HIV clinic (date of first clinic visit)		+		X	X	X	X	X	X	
Retention (attendance at monthly clinic visit)		+		X	X	X	X	X	X	
ART adherence (3-day recall; pharmacy refills)		*+	X	X	X	X	X	X	X	
Plasma HIV-1 RNA level			X		X		X		X	
ACCEPTABILITY										
Qualitative interviews		§					X	X	X	
COST										
Number and type of health facility visits		*+	X	X	X	X	X	X	X	

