Data Management: All data will be collected using an Android tablet and will be stored on encrypted servers at MITU. Research assistants will complete research questionnaires on the tablets at each visit. They will abstract clinical and laboratory information from the HIV Clinic EMR at each study visit and enter the data onto Case Report Forms (CRFs) on tablets. Individuals will be identified by a study ID number and no participant identifying information (name, address) will be recorded on questionnaires or CRFs. The MITU data manager ([name]) will supervise and clean all data and will transfer the data into the NIH approved **REDCap** data management system. The REDCap system is encrypted and password protected and has been used in prior Cornell-MITU NIH supported research.

Quality Control and Assurance: The PI and [name] will oversee data quality control and assurance. They will review all informed consent documents and study eligibility checklist forms. The PI, [name] and [name] will review the REDCap data files for internal validity and completeness and send queries to the data management team in Tanzania each week. The team will respond to queries within one week. Prior to enrollment, the research coordinator and research assistants will verify that the completion of the informed consent form and that all inclusion and exclusion criteria have been met. During the trial, all data collection documents will be verified by the research coordinator. Additionally, the REDCap system for data collection will also perform quality control checks to ensure that all required information are obtained.

Sample Size and Power: We performed sample size (N)/power calculation using the log-rank test for the primary outcome (**survival**) in the two independent study groups. With 500 participants and 10% lost to follow up, we have >80% power with α of 0.05 to detect a 10% to 20% absolute difference in survival between the DARAJA intervention group and the control group across the range of expected survival rates (**Table 4**). We will have 98% power to detect a difference between 75% vs. 90% per our primary hypothesis. This is shown in *italics* in Table 3. Our sample size will also provide reasonable power for important secondary analyses. For example, for secondary aim 1, we will have >80% power to detect most 10% absolute differences for linkage and other steps in the HIV care continuum.

Survival Rates DARAJA vs. Control	Absolute Difference	Power ($\alpha = .05$)

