95% vs. 75%	20%	0.99
90% vs. 75%	15%	0.98
90% vs. 80%	10%	0.87
85% vs. 75%	10%	0.80

Table 4. Power for Different Survival Rate

Data Analysis:

Primary Aim: Survival at 12 months. We will compare survival between the study and control arms using the log-rank test following the intention-to-treat principle. Survival times are measured in days from the date of randomization which will occur on the morning of hospital discharge. This is an individual randomized trial, and we anticipate the two arms will have similar baseline characteristics. Therefore, the primary analysis will be done without adjusting for baseline variables. Since we have one primary outcome, we will test the primary hypothesis without multiple testing adjustments. Statistical tests will be two-tailed, with a significance level of 0.05. If some variables at baseline are notably imbalanced, we will conduct adjusted analyses as secondary or sensitivity analysis using multivariable-adjusted Cox regression and Cochran–Mantel–Haenszel statistics. The results will be summarized in terms of survival rates as well as hazards ratios, along with confidence interval and statistical significance.

Secondary Aim 1: Linkage and other steps in the HIV Care Continuum. Time to linkage will be measured in days from the date of randomization to the first HIV clinic visit. For participants without linkage, follow up time will be censored at the date of lost-to-follow up, death, or study end, whichever happens first. Time to linkage will be compared between groups using the log-rank test. We will conduct adjusted analyses using Cox regression. HIV clinic retention, ART adherence and viral suppression will be treated as binary outcomes at 12 and 24 months. We will compare these outcomes between study arms using the Fisher exact test. We will conduct adjusted analyses using multivariable-adjusted logistic regression and Cochran–Mantel–Haenszel statistics.

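### The stated >80% power for most 10-point differences does not hold for the Fisher-tested care-continuum outcomes unless control rates are high or very low

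*Protocol*

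**What the plan says.** Protocol, Sample Size and Power, bases its survival calculation on the log-rank test ("With 500 participants and 10% lost to follow up") and tabulates it in Table 4. It then extends the assurance to secondary aim 1: "we will have >80% power to detect most 10% absolute differences for linkage and other steps in the HIV care continuum". No calculation accompanies that sentence. The total, the loss and (later) the tests can be found in the Protocol; the control rates cannot.

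Protocol, Data Analysis, Secondary Aim 1, sets the tests. "HIV clinic retention, ART adherence and viral suppression will be treated as binary outcomes at 12 and 24 months", and "We will compare these outcomes between study arms using the Fisher exact test". Linkage is handled differently: "Time to linkage will be compared between groups using the log-rank test".

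The outcome definitions are in the Protocol paragraph on linkage and the care continuum. "Twelve-month retention will be defined as being alive and having a clinic visit between 11 and 13 months". A participant with no RNA measurement counts as a virologic failure. For linkage, "Linkage will be defined as having at least one visit to the outpatient HIV clinic", with no time limit.

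The SAP (Secondary endpoints; Proposed Table 2) keeps Fisher's test at 12 months but removes participants who died or withdrew from all three binary outcomes. It restates only the 98% power for the primary endpoint and does not repeat the secondary power sentence.

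**The concern.** Power for a fixed absolute difference depends strongly on the control rate. It is lowest near 50% and rises towards either end. Both 10-point rows in Table 4 have control survival of 75% or 80%, in the favourable region, and use a log-rank test. Neither feature carries over automatically to Fisher's test on retention, adherence or suppression.

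These outcomes are the pathway through which the intervention is expected to work. A reader told that power exceeds 80% may take a non-significant Fisher result as evidence against a 10-point effect. SAP Proposed Table 2 has counts and a p-value but no interval that would show what the data exclude.

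**Working it through.** **1. The plan's own figures.** Table 4 can be reproduced. With 250 per arm and no loss, take HR = ln(S1)/ln(S0), D = 250(1 − S1) + 250(1 − S0), and power = Φ(√D × (1 − HR)/(1 + HR) − 1.96) (Freedman).

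| Survival | HR | D | Power | Table 4 |
|---|---|---|---|---|
| 95 vs 75 | 0.178 | 75 | 1.00 | 0.99 |
| 90 vs 75 | 0.366 | 87.5 | 0.991 | 0.98 |
| 90 vs 80 | 0.472 | 75 | 0.874 | 0.87 |
| 85 vs 75 | 0.565 | 100 | 0.794 | 0.80 |

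All rows agree within about 1 point, so the survival inputs are read correctly. The secondary sentence has no calculation to reproduce.

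**2. Inputs for the Fisher-tested outcomes.**
- Arms of 250 and 250 (Protocol, Protection of Human Subjects).
- Two-sided 0.05, stated for the primary aim; nothing different is given for secondary aims.
- Control rate p against p + 0.10.
- Control rates: none in the documents, so a range is shown.
- Planned survival of 90% vs 75% (Protocol Summary), used only for the cap in step 4 and the SAP denominators in step 5.

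**3. Exact power, 250 per arm.** Power = Σ over all tables (x, y) that Fisher's test rejects of Bin(x; 250, p + 0.10) × Bin(y; 250, p).

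| Control rate | Power for +10 points |
|---|---|
| 10% | 0.863 |
| 13% | 0.806 |
| 15% | 0.772 |
| 30% | 0.618 |
| 50% | 0.590 |
| 60% | 0.618 |
| 70% | 0.701 |
| 75% | 0.772 |
| 77% | 0.806 |
| 80% | 0.863 |

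Over 15% to 75% the range is 0.59 to 0.77, so a true 10-point difference would be missed 23% to 41% of the time. Power exceeds 0.80 on about 30% of control rates between 0 and 90%. Fisher's conservatism is not the main cause: an uncorrected chi-square test reaches 0.80 on only about 35% of that range.

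**4. The cap from the Protocol's definitions.** Retention requires being alive. Counted over all randomized, control retention is at most the planned 75%, where power is 0.77. The same cap applies to suppression if deaths without an RNA result count as failures.

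**5. The SAP's analysis set.** Excluding deaths leaves 0.90 × 250 = 225 and 0.75 × 250 = 187.5, taken as 187, before withdrawals. The survival cap no longer applies, but the denominators are smaller.

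| Control vs intervention | Power, 187 vs 225 |
|---|---|
| 75 vs 85 | 0.702 |
| 80 vs 90 | 0.799 |
| 85 vs 95 | 0.925 |

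Power exceeds 0.80 on about 22% of control rates between 0 and 90%.

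**6. Difference detectable with 80% power, control rates of 50% to 75%.** With 250 per arm, 12.75 falling to 10.5 points. With 225 vs 187, 14 falling to 11.25 points.

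**7. Linkage.** The Protocol's control figures, 63% and about 70%, are both at one month. The endpoint has no window, and "follow up time will be censored at the date of lost-to-follow up, death, or study end, whichever happens first". Power therefore depends on the first visits accrued over the whole of follow-up and on whether any hazard ratio persists. The documents give neither, so no figure is derived.

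**The case against.** The strongest reply is that no stated calculation has been shown wrong. The sentence says most, names no control rates, and may have had high rates in mind. Weighting every control rate from 0 to 90% equally is the reviewer's device, and so is the 15% to 75% range. This stands in part. The 30% share is descriptive, and adherence among survivors could be high enough for the claim to be true. But for retention the Protocol's own definition and planned survival keep the control rate at or below 75%, so high rates are not available there. Under the SAP they are available, but 80 vs 90 only just reaches 80%.

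A second reply is that the planned survival difference would itself produce gaps above 10 points under the Protocol's definitions. That is correct. If every survivor is retained, 75 vs 90 has power 0.99; if 90% are, 67.5 vs 81 has power 0.92 (250 per arm). These larger gaps are well powered, but the sentence is about 10-point differences.

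Three stronger readings are tempting and not supported:
- **That the 10% loss makes 225 per arm the right basis.** Under the Protocol, participants lost without a visit or RNA result stay in as failures for retention and suppression, so 250 applies. Under the SAP, removals are unequal between arms.
- **That the claim is false for linkage.** The one-month rates do not determine power for a log-rank test with no time window.
- **That the trial as a whole is underpowered.** Table 4 reproduces, and the primary power is unaffected.

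**Conclusion.** The concern holds for retention, adherence and viral suppression. The planned Fisher tests have more than 80% power for a 10-point difference only when the control rate is high or very low, which is not most such differences. At the 75% ceiling for control retention the shortfall is about 3 points (77%). At mid-range control rates it reaches about 21 points (59%).

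The ceiling assumes 75% control survival and all randomized in the denominator; for suppression it also assumes that deaths without a result are failures, which the Protocol implies but does not state. The SAP figures assume planning mortality and no withdrawals, so actual denominators would be smaller if anyone withdraws.

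Severity is minor. The outcomes are secondary, and the SAP, dated May 2023, describes the end line survey as already done. The correction bears on interpretation and cannot alter enrolment.

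**What to change.** Replace the sentence in Protocol, Sample Size and Power, with:

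> For retention, adherence and viral suppression (Fisher exact test, two-sided 0.05), with 250 per arm power for a 10-point difference exceeds 80% only for control rates of about 77% or higher, or 13% or lower. For control rates of 50-75% the difference detectable with 80% power is about 12.75 to 10.5 points with 250 per arm, and about 14 to 11.25 points when deaths are excluded at planning mortality (225 vs 187), before further withdrawals.

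Take linkage out of the >80% statement unless an assumed control rate, a time window and an expected number of first visits are given. Optionally, add a confidence interval for the difference beside the Fisher p-value in SAP Proposed Table 2; it can be computed from the counts already planned.

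The cost is a less favourable stated power for secondary outcomes, a rewritten passage and, if wanted, one table column. Sample size, tests and conduct do not change.
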